## 1. SYNOPSIS

Name of Sponsor/Company: Alkermes, Inc.	
Name of Product: Aripiprazole lauroxil	
Name of Active Ingredient: Aripiprazole	
Title of study: Safety and Tolerability of Initiating Aripiprazole Lauroxil in Subjects with Schizophrenia who are Inadequately Treated with Paliperidone Palmitate or Risperidone Long Acting Injection	
Study Center Multicenter study (United States [US])	
Study Period: Estimated date of first subject's consent: Q4 2015 Estimated date of last subject's last visit: Q3 2017	Phase of Study: 4
Objectives:	
Primary: 

To evaluate the safety, tolerability, and efficacy of aripiprazole lauroxil in subjects with schizophrenia who are inadequately treated with paliperidone palmitate or risperidone long acting injection

	
Secondary: 

To evaluate quality of life, including daily and social functioning, after treatment with aripiprazole lauroxil

To characterize the caregiver and healthcare burden

	
Methodology: 
This is an open-label study in subjects who are switched to aripiprazole lauroxil from paliperidone palmitate or risperidone long acting injection. Subjects will participate for approximately 7 months, including a screening period of up to 30 days, and will be administered 4 to 6 doses of intramuscular (IM) aripiprazole lauroxil. Dosing may occur in monthly (441 mg, 662 mg, or 882 mg) or 6-week (882 mg only) intervals. The dose and frequency of dosing will be at the discretion of the investigator, based on the dose selected, and on dosing instructions.
 
Potential subjects will be evaluated for eligibility according to the inclusion and exclusion criteria at a screening visit and again on Day 1. The first dose of aripiprazole lauroxil will be administered on Day 1. Subjects will receive their first dose of aripiprazole lauroxil no earlier than one week and not later than 6 weeks following their previous injection of paliperidone palmitate or risperidone long acting injection. For subjects who have never taken aripiprazole, two test doses of oral aripiprazole 5 mg will be administered during the screening period. Only subjects who exhibit tolerability to oral aripiprazole (either following test doses or by past experience) are eligible to enroll in the study.
 
On Day 1, qualified subjects will be administered a single IM injection of aripiprazole lauroxil into the gluteal (441 mg, 662 mg, or 882 mg) or deltoid (441 mg only) muscle, according to the dosing instructions. Following the first injection, subjects will return to the study site monthly or every 6 weeks for IM aripiprazole lauroxil administration and outpatient assessments. Additional outpatient assessments may be scheduled at the discretion of the investigator.
 
If a subject must withdraw from the study early, an early termination (ET) visit should be completed
	

using the assessments scheduled for Day 169.

**Number of Subjects Planned:**

This study will enroll approximately 50 subjects.

**Main Criteria for Inclusion:**

Men and women 18 through 65 years of age (inclusive) with a diagnosis of schizophrenia at screening and who have been taking paliperidone palmitate or risperidone long acting injection with inadequate results for at least 3 doses prior to screening may be eligible for this study.

**Product, Dosage, Duration and Mode of Administration:**

Aripiprazole lauroxil in doses of 441 mg (via deltoid or gluteal muscle), 662 mg (via gluteal muscle), or 882 mg IM (via gluteal muscle) will be administered monthly or every 6 weeks (882 mg only). The dose and frequency of dosing will be at the discretion of the investigator, based on the dose selected, and on dosing instructions (as depicted in the table below).

Dose	Dosing Frequency	Site of Intramuscular Injection
441 mg	Monthly	Deltoid or Gluteal
662 mg	Monthly	Gluteal
882 mg	Monthly or every 6 weeks	Gluteal

**Reference Therapy, Dosage, Duration and Mode of administration:**

Not applicable.

**Duration of Study:**

Approximately 7 months.

**Criteria for Evaluation:****Efficacy:**

The following scales will be used to assess efficacy:

- CGI-S and BPRS

**Safety and Tolerability:**

The following safety and tolerability measures will be assessed:

- AEs
- Injection site reactions
- Vital signs (blood pressure, heart rate, respiratory rate, and body temperature), weight, and waist circumference
- Clinical laboratory parameters (chemistry [including prolactin], hematology, and urinalysis)
- C-SSRS responses
- ESRS-A scores

**Quality of Life, Daily and Social Functioning**

The following assessments will be conducted to characterize any change in quality of life, including daily and social functioning:

- Quality of Life Scale (QLS)
- Negative Symptom Assessment-16 (NSA-16)

- Sexual functioning subscale from UKU Side Effect Rating Scale and CSFQ-14 scores
- Personal and Social Performance scale (PSP)
- Total and individual items scores of the Modified -MSQ

**Other Assessments**

The following assessments will be collected to explore potential changes in healthcare burden, cognition, insight, and psychosocial care needs:

- Health economics
  - Total healthcare costs as measured by Treatment Services Review (TSR-6) (Modified for Mental Health)
- Functional Assessment
  - Birchwood Insight Scale (BIS)
- Family Measures
  - Caregiver Quality of Life – Burden Dimensions (CarerQOL-7D) and VAS
  - Burden Assessment Scale
- Investigator- and Caregiver-Rated Cognition
  - Respective New York Assessment of Adverse Cognitive Effects of Neuropsychiatric Treatment (NY-AACENT) subscales
- Substance Use
  - Mini International Neuropsychiatric Interview (M.I.N.I.) Module I (alcohol use disorder)
  - Mini International Neuropsychiatric Interview (M.I.N.I.) Module J (substance use disorder)

**Statistical Methods:**

The safety population will include all subjects who received at least one dose of aripiprazole lauroxil injection. All analyses will be carried out using the safety population.

**Efficacy:**

The change from baseline in CGI-S and BPRS scores at each post-baseline visit will be summarized.

**Safety and Tolerability:**

The number and percentage of treatment emergent adverse events (TEAEs) will be summarized by treatment group and overall by system organ class, and preferred terms within each system organ class. Serious adverse events (SAEs) and AEs resulting in treatment discontinuation will also be summarized.

Observed values and change from baseline in vital signs, clinical laboratory data, and ESRS scores will be summarized

Shift tables and potential clinical significance tables, along with supporting listings, will be provided for selected parameters.

**Analyses of Other Assessments**

Data on quality of life and functional domains including personal, social, and family measures will be summarized using the safety population.

**Sample Size Considerations:**

No formal sample size calculations have been performed. The sample size is based on clinical considerations.

### 3. LIST OF ABBREVIATIONS

The following abbreviations are used in this study protocol.

Abbreviation or Term	Explanation or Definition
AE	adverse event
ALK-P	alkaline phosphatase
ALT	alanine aminotransferase
AST	aspartate aminotransferase
ATC	Anatomical Therapeutic Chemical [classification system]
BIS	Birchwood Insight Scale
BPRS	Brief Psychiatric Rating Scale
CarerQOL-7D	Caregiver Quality of Life – Burden Dimensions
CGI-S	Clinical Global Impressions-Severity
CPK	creatine phosphokinase
CSA	Clinical Study Agreement
CSFQ-14	Changes in Sexual Functioning Questionnaire Short Form
CRO	contract research organization
C-SSRS	Columbia Suicide Severity Rating Scale
DSM-5	Diagnostic and Statistical Manual of Mental Disorders – Fifth Edition
EC	Ethics Committee
ECG	electrocardiogram
eCRF	electronic case report form
EPS	Extrapyramidal symptoms
ESRS-A	Extrapyramidal Symptom Rating Scale - Abbreviated
ET	early termination
FDA	Food and Drug Administration
GCP	Good Clinical Practice
GGP	gamma-glutamyl transferase
HIV	human immunodeficiency virus
HR	heart rate
IB	Investigator's Brochure
ICF	informed consent form
ICH	International Conference on Harmonisation of Technical Requirements for Registration of Pharmaceuticals for Human Use

Abbreviation or Term	Explanation or Definition
IRB	Institutional Review Board
ISR	injection site reaction
LAI	long acting injectable antipsychotic
LDH	lactic dehydrogenase
MedDRA	Medical Dictionary for Regulatory Activities
M.I.N.I.	Mini International Neuropsychiatric Interview
NSA-16	Negative Symptom Assessment-16
NY-AACENT	New York Assessment of Adverse Cognitive Effects of Neuropsychiatric Treatment
PANSS	Positive and Negative Syndrome Scale
PK	pharmacokinetics
QLS	Quality of Life Scale
RR	respiratory rate
SAE	serious adverse event
SAP	statistical analysis plan
SD	standard deviation
TEAE	treatment-emergent adverse event
TSR-6	Sixth edition of the Treatment Services Review
UKU	Udvalg for Kliniske Undersøgelser
ULN	upper limit of normal
VAS	Visual Analog Scale
WHO	World Health Organization

#### 4. INTRODUCTION

Aripiprazole lauroxil is a covalently bonded, non-ester modification of aripiprazole, a second generation atypical antipsychotic agent, to form *N*-lauroyloxymethyl aripiprazole. It is formulated as an extended-release suspension to be administered via intramuscular (IM) injection into the gluteal or deltoid muscle. Conversion of aripiprazole lauroxil to aripiprazole is governed by dissolution of the aripiprazole lauroxil drug crystal from the injection site and subsequent enzyme-mediated cleavage, generating lauric acid and *N*-hydroxymethyl aripiprazole; the covalently bonded hydroxymethyl group *N*-hydroxymethyl aripiprazole dissociates, releasing aripiprazole and formaldehyde.

In clinical trials, treatment with aripiprazole lauroxil demonstrated statistically significant reductions from baseline in Positive and Negative Syndrome Scale (PANSS) total scores at Week 12, compared with placebo. Aripiprazole lauroxil was generally well tolerated for patients with schizophrenia at monthly IM dosing of 441 mg and 882 mg with the most common adverse events being insomnia, akathisia, and headache. This study is designed to demonstrate that 1) the transition from treatment with other long acting injectable antipsychotics (LAIs) to aripiprazole lauroxil is clinically feasible, and that 2) comparative assessments of the safety and tolerability profiles of the respective treatments is clinically important.

Paliperidone palmitate (Invega® Sustenna®) or risperidone long acting injection (Risperdal® Consta®) are commonly prescribed long-acting injectable antipsychotics. Paliperidone palmitate is a prodrug of paliperidone (9-hydroxy risperidone), the active metabolite of risperidone. As potent D2 antagonists, risperidone and paliperidone are pharmacologically distinct from aripiprazole's hypothesized principal mechanism of antipsychotic action, one of high affinity, partial dopamine agonism.

This study is an open label, 7-month prospective evaluation of the safety, tolerability, and efficacy of aripiprazole lauroxil in subjects with schizophrenia inadequately treated with risperidone long acting injection or paliperidone palmitate.

## **5. OBJECTIVES**

### **5.1. Primary Objective**

The primary objective of this study is to evaluate the safety, tolerability, and efficacy of aripiprazole lauroxil in subjects with schizophrenia who are inadequately treated with paliperidone palmitate or risperidone long acting injection.

### **5.2. Secondary Objectives**

The secondary objectives of this study are to:

- Evaluate quality of life, including daily and social functioning, after treatment with aripiprazole lauroxil
- Characterize the caregiver and healthcare burden

## 6. SELECTION AND WITHDRAWAL OF SUBJECTS

Each subject must meet all of the eligibility criteria to be qualified to participate in this study.

### 6.1. Subject Inclusion Criteria

Each subject must meet all of the following inclusion criteria to be qualified to participate in this study.

1. Is willing and able to provide informed consent
2. Is between 18 and 65 years of age, inclusive, at screening
3. Meets either of the following aripiprazole tolerability criteria:
  - Has demonstrated tolerability to test doses of oral aripiprazole during screening; OR
  - Has a history of tolerated use of aripiprazole
4. Has a diagnosis of schizophrenia as defined by Diagnostic and Statistical Manual of Mental Disorders, 5th Edition [DSM-5] ([American Psychiatric Association 2013](#)) criteria at screening
5. Is clinically stable as evidenced by no hospitalizations for acute psychiatric exacerbations within the 2 months prior to screening and prior to initiation on Day 1. Social hospitalizations are not applicable and should not disqualify subjects
6. Has a BPRS score of  $\geq 30$  and  $\leq 45$  at screening
7. Has received at least 3 doses of risperidone long acting injection (Risperdal Consta®) or paliperidone palmitate (Invega Sustenna®) prior to screening (may include the 'loading' dose). Has no antipsychotic medication regimen change for 4 weeks prior to Day 1 (medication or dose level, unless due to tolerability).
8. In the judgment of the investigator, is inadequately responding to or not tolerating long acting injectable (risperidone or paliperidone), and is likely to benefit from a transition to aripiprazole lauroxil
9. Agrees to abide by the contraceptive requirements of the protocol (as defined in [Section 7.4.2](#))
10. Has an identified reliable informant (caregiver), in the opinion of the investigator
11. Resides in a stable living situation, in the opinion of the investigator
12. Is fluent (oral and written) in the language in which standardized tests will be administered, and can be reliably rated

## 6.2. Subject Exclusion Criteria

Each subject must not have any of the following conditions to be qualified to participate in this study.

1. Is currently pregnant or breastfeeding, or is planning to become pregnant during the study
2. Has received Invega Trinza® (3-month formulation of paliperidone palmitate), aripiprazole lauroxil or IM depot aripiprazole within 6 months of screening
3. Has a history of poor or inadequate response to oral or injectable aripiprazole
4. Has participated in a clinical trial involving any investigational product (ie, drug, device, biologic) within the past 3 months, or is currently participating in a clinical trial involving an investigational product
5. Has a history of psychopathology other than schizophrenia as indicated by any of the following:
  - Has a DSM-5 ([American Psychiatric Association 2013](#)) diagnosis of moderate to severe substance use disorder (except tobacco use disorder), within the 12 months prior to screening
  - Has any primary DSM-5 diagnosis other than schizophrenia within the 12 months prior to screening or upon admission (depression, schizoaffective disorder, bipolar disorder, or neurocognitive disorder)
6. In the opinion of the investigator, the subject is a danger to himself/herself or others at screening or upon admission or meets one of the following criteria for elevated suicidal ideation or behavior:
  - At screening (using “Baseline” version of the C-SSRS):
    - Answers “Yes” to items 4 or 5 of the C-SSRS “Suicidal Ideation” section with the most recent episode occurring within the 6 months prior to screening
    - Answers “Yes” to any of the 5 items C-SSRS “Suicidal Behavior” with an episode occurring within the 1 year prior to screening
  - Upon entry (on Day 1) (using “Since Last Visit” version of the C-SSRS):
    - Answers “Yes” to items 4 or 5 of the C-SSRS “Suicidal Ideation”
    - Answers “Yes” to any of the 5 items of the C-SSRS “Suicidal Behavior”
7. Has a history or current evidence of a clinically significant condition or abnormality (including clinical laboratory test results or ECG findings) that in the investigator’s opinion could preclude safe participation in this study, or prevent, limit, or confound protocol specified assessments
8. Has any of the following conditions or abnormalities at screening:
  - In the opinion of the investigator or sponsor has uncontrolled diabetes, heart disease or stroke

- Aspartate aminotransferase (AST) or alanine aminotransferase (ALT) levels  $\geq 3$  times the upper limit of the laboratory reference range at screening
- An absolute neutrophil count  $\leq 1.5 \times 10^3 \mu\text{L}$  (or for black patients with history of “benign neutropenia”, a sustained count of  $\leq 1 \times 10^3 \mu\text{L}$ )
- A platelet count  $\leq 100 \times 10^3 \mu\text{L}$
- Has a QT interval (corrected using the Fridericia formula; QTcF)  $>450$  milliseconds for men or  $>470$  milliseconds for women at screening

9. Has a history of neuroleptic malignant syndrome or clinically significant tardive dyskinesia

10. Is taking both strong CYP2D6 and strong CYP3A4 inhibitors. In addition, patients who are known CYP2D6 poor metabolizers taking strong CYP3A4 inhibitors are excluded

11. Has a positive urine drug test for illicit use of amphetamines, barbiturates, cocaine, methadone, opiates, phencyclidine, at screening. Repeat testing may be performed if positive results cannot be confirmed by a history of presumed active substance use, or use of prescribed medications which may account for the positive urine drug test results

12. Is employed by Alkermes, PPD the investigator, the study center (includes permanent or temporary contract workers and designees responsible for the conduct of the study), or a third-party agent of this study or is immediate family of an employee of Alkermes, PPD the investigator, the study center, or other third-party agent

- Immediate family is defined as a spouse, parent, child, or sibling, whether biological or legally adopted.

### 6.3. Subject Withdrawal

A subject may be discontinued from the study at any time if the subject, investigator, or sponsor determines that it is not in the best interest of the subject to continue participation. Reasons for discontinuation include:

- AE
- Lost to follow-up
- Lack of Efficacy
- Withdrawal by subject
- Non-compliance with study drug
- Other
- Pregnancy
- Protocol deviation
- Study terminated by sponsor

Subjects completing all visits up to and including Day 169 will be considered completers.

If a subject withdraws from the study for any reason, any ongoing AEs will be followed until resolution, until deemed stable by the investigator, or until the subject is deemed by the investigator to be lost to follow-up. If, in the opinion of the investigator, it is necessary to monitor a subject beyond the final study visit, the study period may be extended as necessary. In such instances, the sponsor and the investigator will agree to an acceptable schedule.

In the event that a subject chooses to withdraw from the study, the investigator should make a reasonable effort to ascertain the reason(s) for withdrawal, while fully respecting the subject's rights. Subjects are to be asked to return to the clinic for an ET visit. If the subject fails or refuses to return to the study center, an attempt must be made to contact the subject by telephone in order to assess as many safety and efficacy parameters as possible. All data collected over the telephone must be documented and kept in the subject's record.

The investigator must maintain a record of all subjects who fail to complete the study. The reason for study discontinuation will be made on the appropriate electronic case report form (eCRF). If a subject is lost to follow-up, a reasonable attempt to contact the subject must be made and documented.

#### **6.4. Replacement of Subjects**

[figure not shown]
Subjects who withdraw before completion of the study will not be replaced.

## 7. STUDY DESIGN

### 7.1. Overall Study Design and Plan

This is an open-label study in approximately 50 subjects who are switched to aripiprazole lauroxil from long acting injectable risperidone or paliperidone palmitate. In total, subjects will participate for approximately 7 months, including a screening period of up to 30 days, and will be administered 4 to 6 doses of IM aripiprazole lauroxil (Figure 1). Dosing may occur in monthly (441 mg, 662 mg, or 882 mg) or 6-week (882 mg only) intervals. The dose and frequency of dosing will be at the discretion of the investigator, based on the subject's history, dose selected, and on dosing instructions ([Section 8.1](#)).

**Figure 1: Study Design (ALK9072-A401)**

Potential subjects will be evaluated for eligibility according to the inclusion and exclusion criteria at a screening visit and again on Day 1. The first dose of aripiprazole lauroxil will be administered on Day 1. Subjects will receive their first dose of aripiprazole lauroxil no earlier than one week and not later than six weeks following their previous injection of paliperidone palmitate or risperidone. The cross-tapering from risperidone or paliperidone to aripiprazole lauroxil is facilitated by the gradual disappearance of plasma risperidone/paliperidone while aripiprazole is concomitantly released from the initial IM aripiprazole lauroxil injection.

For subjects who have never taken aripiprazole, two test doses of oral aripiprazole 5 mg will be administered during the screening period. Only subjects who exhibit tolerability to oral aripiprazole (either following test doses or by past experience) are eligible to enroll in the study.

On Day 1, qualified subjects will be administered a single IM injection of aripiprazole lauroxil into the gluteal (441, 662 or 882 mg) or deltoid muscle (441 mg), according to the dosing instructions ([Section 8.1](#)). Following the first injection, subjects will return to the study site monthly or every 6 weeks (882 mg, gluteal IM only) for IM aripiprazole lauroxil administration and outpatient assessments. Additional outpatient assessments may be scheduled at the discretion of the investigator.

Efficacy will be evaluated based on Clinical Global Impressions-Severity (CGI-S) and Brief Psychiatric Rating Scale (BPRS) responses.

Safety and tolerability will be evaluated based on adverse events (AEs), injection site reactions (ISRs), clinical laboratory data, vital sign data, Columbia Suicide Severity Rating Scale (C-SSRS) responses, and Abbreviated Extrapyramidal Symptom Rating Scale (ESRS-A) scores. Potential changes in informant-rated cognition, insight, treatment satisfaction, quality of life, daily and social functioning, caregiver and healthcare burden, and psychosocial care needs following a transition to aripiprazole lauroxil will be examined. Total healthcare costs as measured by TSR-6-(Modified for Mental Health) survey will also be evaluated.

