## 8. TREATMENT OF SUBJECTS

### 8.1. Study Drug Dose and Administration

The initial dose of aripiprazole lauroxil will be selected according to the investigator's judgment and will be prepared and administered in accordance with the Directions for Use.

Depending on individual patient's needs, treatment with aripiprazole lauroxil can be initiated at a dose of 441 mg, 662 mg or 882 mg administered monthly, which corresponds to 300 mg, 450 mg and 600 mg of aripiprazole, respectively. Treatment may also be initiated with the 882 mg dose every 6 weeks.

Subjects will receive their first dose of aripiprazole lauroxil no earlier than one week and not later than 6 weeks following their previous dose of injectable risperidone or paliperidone. Due to safety concerns and the potential for rapid emergence of adverse events including akathisia, dystonia and EPS, oral aripiprazole dosing for 21 days after the initial dose of aripiprazole lauroxil is not recommended. Cross-tapering patients from long acting injectable risperidone or paliperidone palmitate to aripiprazole lauroxil is facilitated by the gradual disappearance of plasma risperidone/paliperidone while aripiprazole is concomitantly released from the initial IM aripiprazole lauroxil injection.

Administer aripiprazole lauroxil either in the deltoid muscle (441 mg dose only) or gluteal muscle (441 mg, 662 mg or 882 mg). See Table 3.

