## **2. SAMPLE SIZE AND STATISTICAL POWER CONSIDERATION**

No formal sample size calculations have been performed. The sample size is based on clinical considerations.

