### 3.7.3. Clinical Laboratory Parameters

Laboratory parameters will be presented in conventional (CN) units. Only scheduled lab parameters will be included in the laboratory results summaries.

Observed values and change from baseline will be summarized by treatment group and overall at each visit for chemistry and hematology parameters. Additionally, the number and percentage of subjects with potentially clinically significant (PCS) results will be presented (and by sex for prolactin). Only subjects with non-PCS values at baseline and PCS at any post-baseline visit will be included in the summary table. All PCS values (including baseline) will be included in supportive listings. For urinalysis, rate of abnormalities will be summarized.

Criteria for PCS are listed in [Table 2](#):

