**3.7.8. Extrapyrarnidal Symptom Rating Scale – Abbreviated (ESRS-A)**

Each subcategory (Parkinsonism, Dystonia, Dyskinesia, Akathisia), and total score of the Abbreviated Extrapyrarnidal Symptom Rating Scale (ESRS-A) will be summarized by treatment group and overall using descriptive statistics.

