## **6.1. Analysis Visit Windows**

For all analyses for this study, the scheduled visit and/or time point from the CRF (ie, CRF visit) will be used as the analysis visit and/or time point. There would be one valid value of assessment kept for each scheduled analysis visit in summary/analysis statistics.

Unless specified otherwise, measurements collected from unscheduled visits, will not be included in the summary tables, except for PCS analysis, and will be included in the subject listings.

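### SAP 6.1 keeps unscheduled ESRS-A and C-SSRS results, and apparently the Month 3 make-up ratings, out of the summary tables

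*Protocol*

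**What the plan says.** Protocol 7.1, in the text under Figure 1, states that "Additional outpatient assessments may be scheduled at the discretion of the investigator". The synopsis and SAP 1.2 say the same. None of them names a trigger or an instrument.

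SAP 6.1 takes the CRF visit as the analysis visit: "There would be one valid value of assessment kept for each scheduled analysis visit". It then rules, unless another section provides otherwise, that "measurements collected from unscheduled visits, will not be included in the summary tables, except for PCS analysis". The same measurements "will be included in the subject listings".

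PCS analysis is defined in three places:
- SAP 3.7.3 and Table 2, for laboratory values, where "the number and percentage of subjects with potentially clinically significant (PCS) results will be presented"
- SAP 3.7.4 and Table 3, for vital signs
- SAP 3.7.5, for weight changes of 7% or more

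For ESRS-A, SAP 3.7.8 plans descriptive statistics on "Each subcategory (Parkinsonism, Dystonia, Dyskinesia, Akathisia), and total score". SAP 3.7.7 counts subjects with C-SSRS ideation or behavior over the whole treatment period.

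Footnote 2 to Protocol Table 1 covers a missed or skipped Month 3 visit. The ESRS-A, prolactin, QLS, NSA-16 and PSP due then are to be done at the subject's next visit, and the footnote calls them unscheduled assessments.

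**The concern.** Safety and tolerability are part of the primary objective, and Protocol section 13 lists ESRS-A and C-SSRS among the measures to be assessed during the study and summarized. The SAP admits unscheduled values where an out-of-range laboratory, vital-sign or weight result matters. It does not do so for the rating scales and gives no reason for the difference.

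Early extrapyramidal symptoms are a risk that the protocol itself recognises. Section 8.1 mentions "the potential for rapid emergence of adverse events including akathisia, dystonia and EPS", although it does so when explaining its position on oral aripiprazole after the first injection. An ESRS-A added in the early weeks would be the instrument's only record of such symptoms for a subject who stays in the study, and it would not be tabulated.

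Three things are at stake: the peak ESRS-A severity visible in the tables, the completeness of the C-SSRS count, and the number of subjects in the Month 3 summaries.

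**Working it through.** There is no planned figure to reproduce. SAP section 2 states that "No formal sample size calculations have been performed", and no power or error rate bears on this point. The check sets the passages side by side and does simple arithmetic on the schedule.

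**1. Does the PCS exception reach the rating scales?** PCS criteria exist for laboratory values, vital signs and weight only. SAP 3.5.1 (CGI-S), 3.5.2 (BPRS), 3.7.7 (C-SSRS) and 3.7.8 (ESRS-A) contain no rule on unscheduled data. SAP 3.7.7 names a period, the overall treatment period, but not a data source, so it does not clearly lift the exclusion. The default in SAP 6.1 therefore governs all four scales.

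**2. The ESRS-A gap.** Inputs are from Protocol Table 1: ratings on Day 1, at Month 3 (target Day 85, window 65-92) and at Month 6/ET (target Day 169, window 149-183).
- Days after Day 1 and before the Month 3 window: 64 − 2 + 1 = 63 (Days 2 to 64).
- Target-day gaps: 85 − 1 = 84 and 169 − 85 = 84.
- Days between the Month 3 and Month 6 windows: 148 − 93 + 1 = 56 (Days 93 to 148).
- Scheduled post-baseline ratings: 2, on either regimen.

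An ESRS-A added in either gap, other than at an ET visit or as a Month 3 make-up (step 4), is unscheduled and reaches listings only.

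**3. C-SSRS.** It is scheduled at every visit, and Protocol 7.3.8 has each later form ask about the time since the last scheduled assessment. A positive result at an unscheduled visit should therefore be reported again at the next scheduled or ET form. It is missed if the subject does not return, or does not report it again.

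**4. Month 3 make-up values.** SAP 6.1 can be read in two ways.
- If the make-up counts as a measurement from an unscheduled visit, it is excluded. Prolactin would still count for PCS.
- If it counts under the visit at which it was done, it falls at Month 4 or 5, where ESRS-A, QLS, NSA-16 and PSP have no scheduled slot.

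Neither reading places it in the Month 3 summary. For ESRS-A, that summary is one of only two scheduled post-baseline ratings.

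**5. CGI-S and BPRS.** Both are rated at every scheduled visit and at ET.
- Monthly dosing: Days 29, 57, 85, 113, 141 and 169, which is 6 ratings 28 days apart.
- Six-weekly dosing with visits skipped: Days 43, 85, 127 and 169, which is 4 ratings 42 days apart.

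Only worsening that comes and goes between visits 28 to 42 days apart escapes the tables.

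**6. How many subjects?** The documents give no rate. As an illustration only, assume that 5% to 20% of about 50 subjects have an added rating for a symptom that settles before the next scheduled one: 50 × 0.05 = 2.5 and 50 × 0.20 = 10, so about 3 to 10 subjects.

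**The case against.** The strongest reply is that little is lost and no planned table is wrong.
- **Listings.** SAP 6.1 itself sends unscheduled values to the subject listings. This stands: a reader might infer that the values vanish from the results, and they do not.
- **Adverse events.** Events are collected continuously (Protocol 7.3.12 and 13.4), and SAP 3.7.1 tabulates them by preferred term and highest severity. Akathisia, dystonia or an exacerbation reported as an event is counted whatever day it occurs. This largely stands. However, event severity has three levels while ESRS-A items run from 0 to 5 over four syndromes, SAP 3.7.1 plans no grouped extrapyramidal summary, and the protocol lists ESRS-A as a measure in its own right.
- **ET visits.** A subject who withdraws early is due the Day 169 assessments, including ESRS-A, CGI-S and BPRS. This stands, and it is why the gap applies only outside ET visits.
- **No stated trigger.** Protocol 7.1 leaves added assessments to discretion. Worsening is a plausible reason in an open-label switch study, but it is an inference.
- **Fixed-time means.** Leaving event-driven readings out of by-visit means is normal practice, and no worst-value table is planned even for scheduled data. This stands for the means. It does not answer the C-SSRS count, which claims to cover a period, or the make-up values, which the protocol requires.
- **C-SSRS look-back and telephone contact.** The look-back, and the attempt under Protocol 6.3 to reach by telephone a subject who does not return for ET, narrow the loss but do not close it.

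**Conclusion.** The point holds in limited form. Under SAP 6.1, an ESRS-A added on Days 2 to 64, other than at an ET visit, enters no ESRS-A summary table. A positive unscheduled C-SSRS is left out of the treatment-period count unless it is reported again on a later scheduled or ET form. The Month 3 make-up values ordered by footnote 2 appear to be left out of the Month 3 tables. That last part needs no assumption about why an assessment was added; it rests only on how SAP 6.1 classes a make-up value.

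A reader might go further and infer that extrapyramidal severity and psychiatric worsening are understated across the primary safety and efficacy results, or that the worst CGI-S and BPRS scores are lost. The documents do not support that. Adverse event tables run independently of visits, CGI-S and BPRS are rated every 28 to 42 days and at ET, and nothing shows that a subject's worst score falls at an added visit.

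The number of subjects affected is unknown; the range of 3 to 10 rests wholly on the assumed 5% to 20%. Treating discretionary assessments as unscheduled visits is the natural reading, but the SAP does not say so. This is a cheap improvement to safety reporting in a descriptive study. It does not show bias in the planned means or tests.

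**What to change.** In SAP 6.1, replace the exception with wording such as:

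*Unscheduled measurements are left out of by-visit summaries. Together with scheduled and ET values, they are used for PCS analysis, for the count of subjects with any post-baseline C-SSRS ideation or behavior, and for worst post-baseline ESRS-A subscale and total scores. A make-up assessment done under footnote 2 of Protocol Table 1, before the Month 6/ET visit, is analysed as Month 3.*

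In SAP 3.7.8, add one summary of the worst post-baseline ESRS-A subscale and total scores and their change from baseline, by switch-reason group and overall. A matching row for CGI-S and BPRS in SAP 3.5 is optional. Leave the other by-visit means and the end-of-treatment t-tests on scheduled values.

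The costs are small:
- A few added table rows, using data already collected.
- Reported peak severity may look slightly less favourable.
- The worst of several readings drifts upward as the number of ratings rises, and more so for subjects seen more often. The summary should therefore be descriptive, with the number of ratings per subject shown.
- A mapped make-up value is late. Against the Day 85 target, the next target visit is Day 113 on monthly dosing (113 − 85 = 28 days) or Day 127 on six-weekly dosing with Month 4 skipped (127 − 85 = 42 days). The listing should flag these values and give the actual study day.
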